7.2.3.1 Criteria for premature patient withdrawal

Patients may voluntarily withdraw from the study or be dropped from it at the discretion of the investigator at any time. Patients may also be withdrawn from the study if any of the following occurs:

- Presence of any medical condition that in the investigator's opinion may affect the safety of the patient.
- Toxicity or appearance of any unacceptable AE that, in the investigator's opinion, may justify treatment withdrawal.

- Concomitant disease that, in the opinion of the investigator, makes it necessary to withdraw the patient.
- Major protocol violations.
- Systematic noncompliance with the study protocol, including the scheduled visits, without any evidence of actions to try to remedy it.
- Pregnancy of a female patient.
- Patient lost to follow-up.
- Use of prohibited medication. Please, refer to [Section 6.3.2](#)
- Reasons for premature discontinuation of eltrombopag displayed at [Section 6.1.2](#)

7.2.4 Follow-up for survival

All patients who discontinue from the study, regardless the reason of discontinuation, will be followed for survival for 24 and 36 weeks, unless they withdraw their consent, die or are lost-to follow-up, in which case will be censored at the last contact/follow-up.

7.3 Assessment types

7.3.1 Efficacy assessments

7.3.1.1 Overall hematologic response rate

The overall response rate corresponds to the percentage of patients who have a hematological response (partial and complete) by 16 weeks after the initiation of eltrombopag.

A partial hematologic response (PR) is defined when any of the following:

- Platelet count $\geq 20,000/\mu\text{L}$ (with platelet transfusion independence), confirmed in two consecutive blood tests separated a minimum of 7 days.
- Absolute neutrophil count (ANC) $\geq 1,000/\mu\text{L}$ (when pretreatment ANC was $< 1,000/\mu\text{L}$) confirmed in two consecutive blood tests separated a minimum of 7 days
- Hemoglobin $\geq 100\text{g/L}$ (when pretreatment Hb was $< 100\text{g/L}$) (with red blood cells (RBC) transfusion independence), confirmed in two consecutive blood tests separated a minimum of 7 days.

A complete response (CR) is defined when all three of the following:

- Platelet count $\geq 100,000/\mu\text{L}$ confirmed in two consecutive blood tests separated a minimum of 7 days
- Absolute neutrophil count (ANC) $\geq 1,500/\mu\text{L}$ (when pretreatment ANC was $< 1,000/\mu\text{L}$), confirmed in two consecutive blood tests separated a minimum of 7 days.
- Hemoglobin $\geq 110\text{ g/L}$ (when pretreatment Hb was $< 100\text{g/L}$), confirmed in two consecutive blood tests separated a minimum of 7 days.

Responses in each hematological lineage separately will be determined at weeks 16, 20, 24, 30 and 36 after the initiation of eltrombopag. In addition, secondary overall hematological

response outcomes (partial and complete) will be determined at 24 and 36 weeks after the initiation of eltrombopag.

Local evaluations will be used for laboratory tests (hematology and biochemistry), and whenever possible the same local laboratory will be used throughout the study so that the comparison is consistent.

7.3.1.2 Supportive care

The need for platelets and red cells transfusions will be monitored at each visit as noted in [Table 7-1](#).

The concomitant use of G-CSF and/or EPO therapy will be recorded at each visit, as outlined in [Table 7-1](#).

7.3.1.3 Overall survival

Overall survival, defined as the time from the date of inclusion until the date of death due to any cause, will be assessed. All patients who discontinue from the study will be followed for survival for 24 and 36 weeks, unless they withdraw their consent, die or are lost-to follow-up, in which case will be censored at the last contact/follow-up.

The survival rate will also be evaluated by the percentage of patients still alive at 24 and 36 weeks.

7.3.2 Safety assessments

Safety will be monitored by assessing physical examination, vital signs and laboratory evaluations, as well as recording of the adverse events at every visit. For details on AEs monitoring and reporting, refer to [Section 8](#).

Significant findings that were present before the signing of informed consent must be included in the Relevant Medical History/Current Medical Conditions page on the patient's CRF. Significant new findings that begin or worsen after informed consent must be recorded on the Adverse Event page of the patient's CRF.

7.3.2.1 Physical examination

An examination of general appearance will be performed at Screening and at scheduled study visits up to Final Visit (or Early Withdrawal), as noted in [Table 7-1](#)

7.3.2.2 Performance status

Performance status or functional impairment will be assessed using the Karnofsky Performance Scale Index at Screening and at scheduled study visits up to Final Visit (or Early Withdrawal), as outlined in [Table 7-1](#).

7.3.2.3 Height and weight

Height in centimeters (cm) will be measured only at Screening. Body weight in kilograms (to the nearest 0.1 kilogram (kg) in indoor clothing, but without shoes) will be measured during the

Screening visit, and at subsequent visits up to Final Visit (or Early Withdrawal), as noted in [Table 7-1](#).

7.3.2.4 Vital signs

Vital signs (blood pressure (BP), respiratory rate, temperature and pulse) will be collected according to the Visit Schedule as outlined in [Table 7-1](#). BP will be taken with the patient in the sitting position after 5 minutes of rest.

7.3.2.5 Clinical safety laboratory evaluations

All laboratory assessments will be performed locally, at the Investigator's site laboratory. For laboratory parameters collection plan, see [Table 7-1](#) and [Table 7-2](#).

Table 7-2 Local clinical laboratory parameters collection plan

Test Category	Test Name
Hematology (screening, week 16, and final visit)	
 - CBC [Hematocrit, Hemoglobin, MCH, MCHC, MCV, Platelets, Red blood cells, White blood cells, Differential (Basophils, Eosinophils, Lymphocytes, Monocytes, Neutrophils)] - Reticulocytes - Direct antiglobulin (Coombs) test (DAT) - Immature platelets (if available) - Lymphocytes subpopulations: CD3, CD4, CD8, CD19, CD56
Hematology (rest of the visits)	
 - CBC [Hematocrit, Hemoglobin, MCH, MCHC, MCV, Platelets, Red blood cells, White blood cells, Differential (Basophils, Eosinophils, Lymphocytes, Monocytes, Neutrophils)] - Reticulocytes - Immature platelets (if available)
Biochemistry Immunology Microbiology Other (Screening, week 16, and final visit)	
 - Bilirubin (Total, Direct), Alkaline phosphatase, AST/GOT, ALT/GPT - Urea, Creatinine, Uric acid, LDH, CL, Na, K, Ca, Mg, Creatine kinase, haptoglobin - Cholesterol (total, LDL, HDL), Triglycerides - Glucose - Albumin, Total Protein, proteinogram, Igs (IgG, A and M) - Folate, Vit B12, Vit D - TSH, T4 (free) - Ferritin, Transferrin, Transferrin saturation index - ANAs - CsA, Tacrolimus, other immunosuppressant drugs levels - Epstein-Barr virus (EBV) and cytomegalovirus (CMV): Viral load in blood test by PCR, if serology positive - AGA
Serology (Screening)	
 - Serology HIV, HBV, HCV

Biochemistry (rest of the visits)	
 - Bilirubin (if abnormal: Total, Direct), Alkaline phosphatase, AST/GOT, ALT/GPT - Urea, Creatinine, Uric acid, LDH, CL, Na, K, Ca, Mg, Creatine kinase, haptoglobin
Urine (Screening)	
 - Sediment and systematic analysis
Chimerism in peripheral blood (Screening)	
Blood smear (At screening/baseline, monthly up to week 24 and thereafter every 6 weeks, and at Final visit (or Early withdrawal), or anytime if considered necessary)	
 - Including study of schistocytes (if present)

7.3.2.6 Pregnancy and assessments of fertility

Women of childbearing potential must undergo a serum pregnancy test at screening to confirm eligibility in the trial. Subsequently, urine or serum pregnancy tests should be performed in women of childbearing potential at weeks 4, 8, 12, 16, 20, 24, 30, 36 and 40.

7.3.2.7 12-lead ECG

A standard 12-lead ECG will be obtained for each patient during the study as per Description of study visits ([Table 7-1](#)). Baseline ECGs will be obtained at Screening. All 12-lead ECGs obtained at 24 weeks and Final Visit will be compared with this pre-study treatment 12-lead ECG.

Interpretation of the tracing must be made by a qualified physician and documented on the ECG CRF page. Each ECG tracing should be labeled with the study number, patient initials (where regulations permit), patient number, date, and kept in the source documents at the study site. Clinically significant abnormalities present when the patient signed informed consent should be reported on the Medical History CRF page. Clinically significant findings must be discussed with Novartis prior to enrolling the patient in the study. New or worsened clinically significant findings occurring after informed consent must be recorded on the Adverse Events CRF page.

7.3.2.8 Ophthalmological monitoring

The ophthalmic exam should include the retina, blood vessels, optic disc/nerve. If the presence of a cataract(s) is suspected, a slit lamp examination is required. Ophthalmic exams will be performed at Screening, week 24 and at Final Visit according to [Table 7-1](#).

Significant findings that were present prior to the signing of informed consent must be included in the Medical History page on the patient's eCRF. Significant new findings that begin or worsen after informed consent must be recorded on the Adverse Event page of the patient's eCRF.

7.3.4 Resource utilization

Not applicable.

7.3.5 Patient reported outcomes

Not applicable.

8 Safety monitoring and reporting

8.1 Adverse events

8.1.1 Definitions and reporting

An adverse event is defined as the appearance of (or worsening of any pre-existing) undesirable sign(s), symptom(s), or medical condition(s) that occur after patient's signed informed consent has been obtained.

Abnormal laboratory values or test results occurring after informed consent constitute adverse events only if they induce clinical signs or symptoms, are considered clinically significant, require therapy (e.g., hematologic abnormality that requires transfusion or hematological stem cell support), or require changes in study medication(s).

Adverse events that begin or worsen after informed consent should be recorded in the Adverse Events CRF. Conditions that were already present at the time of informed consent should be recorded in the Medical History page of the patient's CRF. Adverse event monitoring should be continued for at least 30 days (or 5 half-lives, whichever is longer) following the last dose of study treatment. Adverse events (including lab abnormalities that constitute AEs) should be described using a diagnosis whenever possible, rather than individual underlying signs and

symptoms. When a clear diagnosis cannot be identified, each sign or symptom should be reported as a separate Adverse Event.

Adverse events will be assessed according to the Common Terminology Criteria for Adverse Events (CTCAE) version 4.03.

If CTCAE grading does not exist for an adverse event, the severity of mild, moderate, severe, and life-threatening, corresponding to Grades 1-4, will be used. CTCAE Grade 5 (death) will not be used in this study; rather, information about deaths will be collected through a Death form

The occurrence of adverse events should be sought by non-directive questioning of the patient (subject) during the screening process after signing informed consent and at each visit during the study. Adverse events also may be detected when they are volunteered by the patient (subject) during the screening process or between visits, or through physical examination, laboratory test, or other assessments. As far as possible, each adverse event should be evaluated to determine:

1. The severity grade (CTCAE Grade 1-4).
2. Its duration (Start and end dates or ongoing).
3. Its relationship to the study treatment
4. Action taken concerning study or investigational treatment (none, dose adjusted, temporarily interrupted, permanently discontinued, unknown, not applicable)
5. Whether medication or therapy was given (no concomitant medication/non-drug therapy, concomitant medication/non-drug therapy).
6. Outcome (not recovered/not resolved, recovered/resolved, recovering/resolving, recovered/resolved with sequelae, fatal, unknown)
7. Whether it is serious, where a serious adverse event (SAE) is defined as in Section 8.2.1

All adverse events should be treated appropriately. If a concomitant medication or non-drug therapy is given, this action should be recorded on the Adverse Event CRF.

Once an adverse event is detected, it should be followed until its resolution or until it is judged to be permanent, and assessment should be made at each visit (or more frequently, if necessary) of any changes in severity, the suspected relationship to the study treatment, the interventions required to treat it, and the outcome.

Progression of malignancy (including fatal outcomes), if documented by use of appropriate method (for example, as per RECIST criteria for solid tumors or as per Cheson's guidelines for hematological malignancies), should not be reported as a serious adverse event.

Adverse events separate from the progression of malignancy (example, deep vein thrombosis at the time of progression or hemoptysis concurrent with finding of disease progression) will be reported as per usual guidelines used for such events with proper attribution regarding relatedness to the drug.

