Cataracts were observed in toxicology studies of eltrombopag in rodents but have not been reported at significant rates over control groups in human trials. In controlled studies in thrombocytopenic patients with HCV receiving interferon therapy (n = 1439), progression of pre-existing baseline cataract(s) or incident cataracts was reported in 8% of the eltrombopag group and 5% of the placebo group. Retinal hemorrhages, mostly grade 1 or 2, have been reported in HCV patients receiving interferon, ribavirin and eltrombopag (2% of the eltrombopag group and 2% of the placebo group). Hemorrhages occurred on the surface of the retina (preretinal), under the retina (subretinal), or within the retinal tissue. Ophthalmological examination (see [Section 7.3.2.8](#)[7.3.2.8](#)) should be performed at baseline, 24 weeks, and also at Final Visit (or Early Withdrawal). Eltrombopag continuation should be re-considered if suspected cataract development or worsening, or in case of retinal hemorrhages. In clinical trials of eltrombopag in SAA cataracts have not been reported. There is no evidence of cataracts in PGF.

Bone marrow reticulin formation and risk of bone marrow fibrosis

Eltrombopag may increase the risk for development or progression of reticulin fibers within the bone marrow. The relevance of this finding, as with other TPO-R agonists, has not been established yet.

If immature or dysplastic cells not linked to primary disease are observed, peripheral blood smears should be examined for new or worsening morphological abnormalities (e.g., teardrop and nucleated red blood cells, immature white blood cells) or cytopenia(s). If the patient develops new or worsening morphological abnormalities and cytopenia(s) not linked to primary disease, treatment with eltrombopag should be discontinued. A bone marrow biopsy must be considered, including staining for fibrosis.

Progression of existing myelodysplastic syndrome

TPO-R agonists are growth factors that lead to thrombopoietic progenitor cell expansion, differentiation and platelet production. The TPO-R is predominantly expressed on the surface of cells of the myeloid lineage. For this class of TPO-R agonists, there is a concern that they may stimulate the progression of existing hematopoietic malignancies such as myelodysplastic syndrome.

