In clinical studies with a TPO-R agonist, romiplostim and eltrombopag, in patients with MDS, cases of transient increases in blast cell counts were observed and cases of MDS disease progression to AML were reported.

In the CETB115AUS01T study, eltrombopag in combination with IST was assessed in patients with SAA. Published results indicate that clonal cytogenetic evolution with dysplastic changes occurred at a similar frequency compared to NIH historic experience with standard IST (10-15%) (Townsley et al., 2017). All patients should be monitored regularly for new or worsening morphological abnormalities or cytopenia(s), and may require bone marrow evaluation, as clinically indicated.

Eltrombopag should be discontinued in case of suspected myeloproliferation not linked to the primary disease or if there is a suspected myeloproliferation due to eltrombopag treatment.

Bleeding events after study drug discontinuation

Following discontinuation of eltrombopag, platelet counts return to baseline levels within 2 weeks in the majority of patients, which increases the bleeding risk and, in some cases, may lead to bleeding. Platelet counts should be monitored as per protocol following discontinuation of eltrombopag.

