8.1.3 Adverse events of special interest

Adverse events of special interest (AESI) are defined as events (serious or non-serious) which are ones of scientific and medical concern specific to the sponsor's product or program, for which ongoing monitoring and rapid communication by the investigator to the sponsor may be appropriate. Such events may require further investigation to characterize and understand them.

Adverse events of special interest are defined by an ongoing review of the safety data. AESIs are discussed in detail in the Investigator Brochure.

The AESIs for this study are:

- Bleeding events
- Hepatobiliary events
- Renal related events
- Cataract-related events
- Thromboembolic events
- Hematological malignancy
- Abnormal bone marrow analysis/cytogenetic abnormality

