8.2 Serious adverse events

8.2.1 Definitions

Serious adverse event (SAE) is defined as one of the following:

- Is fatal or life-threatening

- Results in persistent or significant disability/incapacity
- Constitutes a congenital anomaly/birth defect
- Is medically significant, i.e., defined as an event that jeopardizes the patient or may require medical or surgical intervention to prevent one of the outcomes listed above
- Requires inpatient hospitalization or prolongation of existing hospitalization,
- Note that hospitalizations for the following reasons should not be reported as serious adverse events:
 - Routine treatment or monitoring of the studied indication, not associated with any deterioration in condition
 - Elective or pre-planned treatment for a pre-existing condition that is unrelated to the indication under study and has not worsened since signing the informed consent
 - Social reasons and respite care in the absence of any deterioration in the patient's general condition
- Note that treatment on an emergency outpatient basis that does not result in hospital admission and involves an event not fulfilling any of the definitions of a SAE given above is not a serious adverse event

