8.2.2 Reporting

To ensure patient safety, every SAE, regardless of suspected causality, occurring after the patient has provided informed consent and until at least 30 days after the patient has stopped study treatment must be reported to Novartis within 24 hours of learning of its occurrence.

Any SAEs experienced after these 30 days period should only be reported to Novartis if the investigator suspects a causal relationship to the study treatment. Recurrent episodes, complications, or progression of the initial SAE must be reported as follow-up to the original episode within 24 hours of the investigator receiving the follow-up information. An SAE occurring at a different time interval or otherwise considered completely unrelated to a previously reported one should be reported separately as a new event.

Information about all SAEs is collected and recorded on the Serious Adverse Event Report Form; all applicable sections of the form must be completed in order to provide a clinically thorough report. The investigator must assess and record the relationship of each SAE to each specific study treatment (if there is more than one study treatment), complete the SAE Report Form in English, and send the completed, signed form by email ([contact]) within 24 hours to Novartis patient safety department:

The telephone, email or telefax number of the contact persons in the local department of Novartis patient safety, specific to the site, are listed in the investigator folder provided to each site. The original copy of the SAE Report Form and the fax confirmation sheet must be kept with the case report form (CRF) documentation at the study site.

Follow-up information is sent to the same contact(s) to whom the original SAE Report Form was sent, using a new SAE Report Form stating that this is a follow-up to the previously reported SAE and giving the date of the original report. Each re-occurrence, complication, or

progression of the original event should be reported as a follow-up to that event regardless of when it occurs. The follow-up information should describe whether the event has resolved or continues, if and how it was treated, whether the blind was broken or not, and whether the patient continued or withdrew from study participation.

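### Documented progression of malignancy, fatal and suspected drug-related cases included, is exempt from SAE reporting although it is a stated class concern; relapse is left undefined

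*Protocol*

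**What the plan says.** The exemption stands in Protocol section 8.1.1. Its subject is "Progression of malignancy (including fatal outcomes), if documented by use of appropriate method", and it concludes: "guidelines for hematological malignancies), should not be reported as a serious adverse event". The paragraph after it keeps events separate from the progression, such as a thrombosis occurring at the same time, under the usual reporting rules.

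Other parts of the protocol bear on the same events:

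- Section 6.2.3, on this class of drugs: "there is a concern that they may stimulate the progression of existing hematopoietic malignancies such as myelodysplastic syndrome". It adds that, in MDS patients given romiplostim or eltrombopag, "cases of MDS disease progression to AML were reported".
- Section 8.1.3 lists "Hematological malignancy" among the AESIs. It says that rapid communication to the sponsor may be appropriate, but sets no deadline.
- Section 8.2.1 opens the SAE definition with "Is fatal or life-threatening" and has no carve-out for malignancy.
- Section 8.2.2 requires reporting within 24 hours for "every SAE, regardless of suspected causality, occurring after the patient has provided informed consent" and until at least 30 days after treatment stops. SUSARs, which are serious by definition, go on to the authorities.
- Section 10.5.2.2 lists and tabulates deaths reportable as SAEs and non-fatal SAEs.

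**The concern.** Exempting progression from SAE reporting is reasonable where progression is the efficacy outcome and is captured there. That reason is absent here. The condition under study is poor graft function, and Table 3-1 has no relapse or progression endpoint. Active malignancy and progression of the underlying disease are excluded at entry (section 5.2), while SAP section 6.4 lists AML, ALL and MDS among the underlying diagnoses. A malignancy that returns or advances on study is therefore a safety outcome, and of the kind the protocol says the drug class may promote.

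Two things are at stake. One is speed: the sponsor need not receive such an event within 24 hours, even if it is fatal and the investigator suspects the drug. The other is the SAE summary, which would omit serious cases of a named concern.

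**Working it through.** The plan gives no figure to reproduce on this point; the check is a comparison of texts.

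**1. Scope of the exemption.** It covers documented progression of malignancy, includes fatal outcomes, and refers to hematological malignancies by name. It has no exception for suspected causality.

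**2. Against the SAE rules.** Item 7 of the AE assessment list in section 8.1.1 takes its definition of seriousness from section 8.2.1, under which a fatal event is serious. Later in section 8.1.1, a fatal progression is taken out of SAE reporting. Sections 8.2.1 and 8.2.2 neither repeat nor limit the exemption.

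**3. Events covered.** Section 6.1.2 separates three situations: new clonal cytogenetic abnormalities, development of MDS or AML, and relapse of the previous hematological disease.

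| Event on study | Named as exempt in 8.1.1? | Consequence |
|---|---|---|
| Documented progression of malignancy | Yes | Outside SAE reporting |
| New MDS or AML, new clonal abnormality | No | Ordinary SAE rules apply |
| Relapse of the transplanted disease | Not stated | Depends on how the site reads progression |

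Because patients enter without active malignancy, the undefined third row may matter most in practice.

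**4. What an exempt event misses.** The 24-hour report and the SUSAR route (both section 8.2.2), and the SAE and death listing (section 10.5.2.2).

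**5. Where it can still appear.**

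- AE record: section 8.1.1 does not prohibit recording progression as an AE or AESI.
- AE analysis: section 10.5.2.2 lists all safety data and summarizes treatment-emergent AEs. SAP section 9 tabulates all AEs by preferred term, severity, relationship and outcome, with fatal as one outcome. AESI is a single yes/no item there, not broken down by category.
- Deaths: the Death form (section 8.1.1) and all-cause overall survival (section 7.3.1.3, SAP section 10.6), which is not analyzed by cause.
- Withdrawal: SAP section 7 tabulates reasons, without a specific category for relapse or progression.

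**6. Scale.** Planned enrollment is 33 (section 4.1). If all 33 are treated, one patient is 1/33 = 0.030, or 3.0 percentage points of the patient-level SAE rate. This applies only when the patient has no other SAE; otherwise that rate does not move. The number of patients affected cannot be derived, because neither document gives a relapse or progression rate.

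**The case against.** The strongest reply is that a specific carve-out from a general definition is not in itself a contradiction. Section 8.2.1 has exclusions of its own, for certain hospitalizations. AESIs may be serious or non-serious, so an event can be an AESI without being an SAE. The safety analysis also reaches well beyond SAEs, deaths are collected separately, and serious events accompanying the progression remain reportable.

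Much of this stands. A reader might infer that these events vanish from the safety data; the routes in step 5 show otherwise. A reader might also infer that every relapse and every new MDS or AML is exempt. The text does not support that: new MDS or AML is not named, and relapse is not equated with progression.

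The reply does not restore prompt reporting. AESI status carries no deadline, the Death form and overall survival do not trigger expedited review, and the SUSAR route requires seriousness. Nor does it supply a reason for the exemption in a trial that does not measure progression as an outcome.

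**Conclusion.** The concern holds in a bounded form. Followed as written, section 8.1.1 keeps documented progression of malignancy, including fatal and suspected drug-related cases, out of SAE reporting, on an outcome the protocol itself names as a concern. What is lost is the 24-hour report, the SUSAR route and the place in the SAE and death listing, not the event itself. The undefined status of relapse adds a second weakness: two sites may handle the same event differently, which makes the SAE counts hard to interpret.

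A reader might multiply 33 by a plausible relapse rate to obtain a number of omitted patients. The documents provide no rate, and not every relapse need meet a seriousness criterion, so such a count would only restate the assumption. The conclusion rests on the wording and does not depend on how many cases occur. It should be corrected, but it does not affect the primary analysis.

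**What to change.** Delete the exemption from Protocol section 8.1.1, or restrict it so that it does not cover hematological malignancy, which is an AESI. State that relapse or progression of the underlying disease, and new MDS or AML, are reported and tabulated as both SAE and AESI when they meet a criterion of section 8.2.1. Reconcile sections 8.1.1, 8.1.3, 8.2.1 and 10.5.2.2 accordingly, and carry the tabulation into SAP section 9.

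The cost is a short written amendment, with the approvals that section 12.1 requires, and a few more SAE forms. Treatment, endpoints and sample size are unchanged.
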